Protocol Title: An Open Label, Randomized Phase 2 Trial of Pomalidomide/Dexamethasone With or Without Elotuzumab in relapsed and refractory Multiple Myeloma

Investigational Product(s), Dose and Mode of Administration, Duration of Treatment with Investigational Product(s):

See **Study Schema** for details

Control Arm

Pomalidomide: 4 mg PO QD Days 1-21 of each cycle

Dexamethasone:

- Subjects \leq 75 years old: 40 mg PO Days (1, 8, 15 and 22) of each cycle
- Subjects $>$ 75 years old: 20 mg PO Days (1, 8, 15 and 22) of each cycle

Elotuzumab Arm

Elotuzumab:

- Cycle 1 - 2: 10 mg/kg IV Days 1, 8, 15 and 22 of each cycle
- Cycle 3 and beyond: 20mg/kg IV Day 1 of each cycle

Pomalidomide: 4 mg PO QD Days 1-21 of each cycle

Dexamethasone: Days 1, 8, 15 and 22 of each cycle

- Subjects \leq 75 years old: weeks with elotuzumab dosing: 28 mg PO + 8 mg IV and 40 mg PO on non-elotuzumab dosing weeks
- Subjects $>$ 75 years old: weeks with elotuzumab dosing: 8 mg PO + 8 mg IV and 20 mg PO on non-elotuzumab dosing weeks

A cycle is defined as 28 days. Treatment with study drug continues until disease progression, unacceptable toxicity (adverse event related to study drug), or subject meets other criteria for discontinuation of study drug outlined in [Section 3.5](#).

Study Phase: 2

[figure not shown]
Primary Objective:

- To compare progression free survival (PFS) between treatment arms

Secondary Objectives:

- To compare objective response rate between treatment arms
- To compare overall survival between treatment arms

Study Schema

Study Population:

Subjects who are diagnosed with relapsed and refractory multiple myeloma defined as:

- 1) Must have received ≥ 2 prior lines of therapy (See [Appendix 1](#)) which must have included at least 2 consecutive cycles of lenalidomide and a proteasome inhibitor alone or in combination.
- 2) Documented refractory or relapsed and refractory (R/R) multiple myeloma
- 3) Refractory (progressed on or within 60 days of treatment) to their last treatment.
- 4) Subjects must have failed treatment with a proteasome inhibitor and lenalidomide in one of the following ways.
 - a) “Refractory” to proteasome inhibitor and lenalidomide, and to their last treatment.
 - b) “Relapsed and refractory”= patients had achieved at least a partial response to previous treatment with proteasome inhibitor or lenalidomide, or both, but progressed within 6 months, and were refractory to their last treatment

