5.1 Progression-Free Survival

The primary objective of the study is to compare the progression-free survival between the treatment arms in all randomized subjects. The number of events and power of this study were calculated assuming an exponential distribution for PFS in each arm.

The study will require at least 71 PFS events (progressions or deaths), for a two-sided experiment-wise $\alpha = 0.2$ log-rank test, to show a statistically significant difference in PFS between the treatment arms with 85% power when the true hazard ratio of the experimental arm to the control arm is 0.57. This is equivalent to demonstrating an improvement in median PFS from 4.0 months in the Pd arm⁹ to a median PFS of 6.8 months in the E-Pd arm.¹ A total of 105 subjects are to be randomized. Assuming approximately 10% of subjects may be lost to follow-up for the primary endpoint data, an additional 9 subjects would be randomized in the study. It is estimated that it would take approximately 9 months for full accrual of 114 subjects (assuming a fixed accrual rate of 13 subjects per month) and another 6 months to obtain the required number of events.

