7.9 Pharmacogenomic Analysis

The relationship between elotuzumab effect on PFS and high risk cytogenetic abnormality will be explored through Cox regression modeling. The following analyses may be conducted depending on the number of subjects with available biomarker data in the trial. A separate model will be produced for each of the following FISH/cytogenetic abnormalities, which will be categorized as positive/negative:

- t(4:14)
- t(14:16)
- del 17p
- del(1q)
- del(1p)
- t(6:14)

Each model will contain treatment, FISH factor and a term for treatment by FISH/cytogenetic factor interaction. If treatment by FISH/cytogenetic factor interaction is not significant at the five percent level it will be excluded from the model. In addition, the treatment effect (median PFS along with corresponding HRs, and 95% CIs) may be computed separately, in the positive and negative groups. A similar analysis may be conducted to evaluate the effect on ORR using a logistic regression model.

Similar analyses, as described above, will be conducted to evaluate the relationship between baseline SLAMF7 expression on MM cells and NK cells with efficacy (PFS or ORR).

The level of SLAMF7 protein expression at baseline and at progression, and the change in SLAMF7 level, from baseline to progression, will be summarized, by arm, using descriptive statistics.

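### SAP 7.9 drops the treatment-by-marker interaction unless p < 0.05, a weak test here, and no readable text commits to an interval for the difference in effect afterwards

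*SAP*

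**What the plan says.** SAP 7.9 describes an exploratory analysis, to be run if enough subjects have biomarker data. One Cox model for PFS is fitted per FISH marker, with treatment, marker and their interaction. The markers are t(4;14), t(14;16), del 17p, del(1q), del(1p) and t(6;14). Then: "If treatment by FISH/cytogenetic factor interaction is not significant at the five percent level it will be excluded from the model". The next sentence is permissive: medians, HRs and 95% CIs "may be computed separately, in the positive and negative groups". ORR may be treated similarly by logistic regression.

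The method carries over to the drug target: "Similar analyses, as described above, will be conducted to evaluate the relationship between baseline SLAMF7 expression on MM cells and NK cells with efficacy". SAP 7.9 also commits to descriptive summaries of SLAMF7 level by arm at baseline and progression. Those do not show the treatment effect by SLAMF7 level.

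SAP 7.5.1.2 separately commits to a forest plot of the PFS hazard ratio with 95% CI in each subgroup category, with no interaction test as a condition. Its list includes del 17p, t(14;16), t(4;14), del(1q) and del(1p). It does not include t(6;14) or SLAMF7. SAP 7.5.2.1 and 7.5.3 repeat the subsets for ORR and OS.

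**The concern.** The interaction coefficient is the answer to the question that 7.9 poses. Removing it because it is not significant treats absence of evidence as evidence of a common effect, and the reduced model then assumes no effect modification. With a test this weak, that would happen in most trials even if a marker abolished the effect. For planning a later trial, the useful output is an interval for how much the effect could differ by marker. The readable text does not promise that interval for any marker once the term is out.

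**Working it through.** **Inputs from the documents**
- Events and design effect: 71 PFS events "for a two-sided experiment-wise $\alpha = 0.2$ log-rank test", with "85% power when the true hazard ratio of the experimental arm to the control arm is 0.57" (SAP 5.1).
- Retention level: 5% (SAP 7.9), two-sided because SAP 7.5 makes all p-values two-sided.

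**Assumptions, because the documents do not give the figure**
- Allocation 1:1 (no ratio is readable).
- Marker-positive share of events, p: 10% to 50%.
- All 71 events have marker data.
- HR 1.00 in marker-positive subjects.

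**The plan's own figure.** With ln 0.57 = -0.562, z(0.90) = 1.282 and z(0.85) = 1.036:
- Schoenfeld: 4 × (1.282 + 1.036)² / 0.562² gives 69 events after rounding up.
- Freedman: (1.282 + 1.036)² × (1.57/0.43)² gives 72 events.
- Schoenfeld power at 71 events: 86.1%.

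So 71 events and 85% power reproduce.

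**Power of the interaction test.** SE of the log ratio of hazard ratios = sqrt(4 / (71 × p × (1 - p))). With z = effect / SE, power = Φ(z - 1.96) + Φ(-z - 1.96).
- Scenario A: HR 0.57 holds in marker-negative subjects, so the effect is 0.562.
- Scenario B: 0.57 is the average over all subjects, so the marker-negative log HR is ln 0.57 / (1 - p) and the effect is 0.562 / (1 - p).

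| p | SE | z, A | Power, A | z, B | Power, B |
|---|---|---|---|---|---|
| 10% | 0.791 | 0.71 | 11.0% | 0.79 | 12.4% |
| 20% | 0.593 | 0.95 | 15.7% | 1.18 | 22.0% |
| 30% | 0.518 | 1.09 | 19.2% | 1.55 | 34.1% |
| 50% | 0.475 | 1.18 | 22.0% | 2.37 | 65.8% |

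The chance that a true loss of effect is dropped is one minus power. At 10% and 20% that is 89% and 84% in A, and 88% and 78% in B.

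**Simulation check of A.** Cox interaction model, 114 subjects, uniform 9-month accrual, control median 4.0 months, cut at the 71st event, 1,400 to 2,000 replicates per prevalence. The term was retained in 11.7% (p = 10%), 13.0% (15%), 19.4% (30%) and 21.6% (50%) of trials.

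**Sensitivity in A**
- Rarer markers: 8.1% at p = 5% and 6.9% at p = 3%.
- Incomplete marker data, p from 10% to 50%: 9.8% to 18.6% with 57 events, 9.2% to 16.9% with 50.
- 2:1 allocation: 10.3% to 20.1%.
- Looser retention level, at p = 10%, 20% and 50%: 18.4%, 24.7% and 32.5% at 0.10; 30.7%, 38.2% and 46.8% at 0.20.

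A looser level does not cure the problem. Reporting the estimate does.

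**What each marker keeps if the term is dropped**

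| Marker | Committed HR by marker group | Committed interval for the difference |
|---|---|---|
| del 17p, t(14;16), t(4;14), del(1q), del(1p) | Yes, SAP 7.5.1.2 | No |
| t(6;14) | No, optional in 7.9 | No |
| SLAMF7 | No, optional in 7.9 | No |

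**The case against.** A reader might infer that a marker which abolishes the effect would usually be reported as one common hazard ratio. The documents do not support that. It is true of the reduced 7.9 model only. For five of the six FISH markers SAP 7.5.1.2 shows both marker groups whatever the interaction test says, the subsets recur for ORR and OS, and SAP 8.7 puts the subset figures in the topline outputs.

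A reader might also infer that the interaction estimate will go unreported. SAP 7.9 says that the term leaves the model. It does not forbid reporting the full fit, and the marker-group HRs are permitted whatever the p-value. The gap is the lack of a commitment.

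Third, 11% to 22% is not a property of this trial. SAP 5.1 states 0.57 for the experimental against the control arm, so scenario B is at least as natural as A. At 50% prevalence it gives 66% power, although it then needs an HR of 0.57² = 0.32 in marker-negative subjects. This limits the power argument to markers at or below about 20%.

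Fourth, SLAMF7 is an expression level and 7.9 gives no cut-off for it, so the binary calculation is only an analogue. Protocol 8.4.5 (Biomarker Analyses) is listed in the contents but its text is not readable, so it cannot be said that no mandatory SLAMF7 analysis exists.

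Fifth, 5% is not an inconsistency with the 0.2 used for PFS, ORR and OS. A stricter level for several unadjusted exploratory tests is defensible, and SAP 7.5.1 sets its own 0.10 for the Gail-Simon test.

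Last, sparse markers may not be estimable. At 10% prevalence about 11 of 114 subjects and 7 of 71 events are marker-positive across both arms. This stands and calls for an estimability condition. None of these points justifies the exclusion rule.

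**Conclusion.** The concern holds in a limited form. The rule removes the term that answers the section's question, using a test with at most about 22% power for markers at or below 20% prevalence in either scenario. A complete loss of effect would then leave the 7.9 model in roughly 78% or more of trials. This rests on 71 events with marker data, 1:1 allocation and the stated hazard ratios. At higher prevalence the answer depends on the scenario.

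For the five markers in the forest plot, the loss is an interval for the difference in effect; two separate subgroup intervals do not supply it. For t(6;14) and for SLAMF7, which Protocol 5.6.1 names as the elotuzumab target, neither that interval nor marker-group HRs are committed in the readable text. Severity is low, because the analysis is exploratory and no primary or secondary conclusion depends on it.

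**What to change.** In SAP 7.9:
1. Delete the exclusion sentence.
2. Wherever the model is fitted and estimable (events in both arms of both marker groups), report the ratio of hazard ratios with 80% and 95% CIs, whatever the interaction p-value. Do the same with the ratio of odds ratios where ORR is analysed. Where the model is not estimable, say so.
3. Make the marker-group HRs mandatory instead of optional under the same condition, above all for t(6;14) and SLAMF7.
4. For SLAMF7, fix the cut-off before the analysis or report the interaction on the continuous scale.
5. Label these intervals as exploratory and unadjusted for multiplicity.

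The cost is SAP wording: the full model has to be fitted anyway before the term can be tested. The downside is a set of wide intervals, which is why the label is needed.

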7.10 Health Related Quality of Life

The analyses of health related quality of life data will be conducted concurrently with the PFS analyses.

Two quality of life (QoL) questionnaires will be used: the M.D. Anderson Symptom Inventory Multiple Myeloma module MDASI-MM which measures symptoms, and the EuroQol Group's EQ-5D which measures utilities, and is a preference-based measure of health status.

The EQ 5D is a 5-item questionnaire and a “thermometer” visual analogue scale ranging from 0 (worst imaginable health state) to 100 (best imaginable health state) that will be administered at the same intervals as the other PRO instruments, including at the Screening Visit to assess the comparability of the groups at study initiation.

The MDASI-MM module is a valid instrument that asks patients to rate 13 symptoms (“core” items) and 6 symptom-related interference items that are common across cancer types and treatments. It also assesses 7 multiple myeloma-specific symptom items: bone aches, muscle weakness, sore mouth/throat, rash, difficulty concentrating, constipation, and diarrhea.

The key PRO endpoints to be included in the exploratory objectives are the pain, bone aches, and fatigue scores of the MDASI-MM scale in addition to the EQ-5D visual analog scale. The mean change in PRO scores between baseline and each post-baseline assessment will be summarized by treatment arm.

The remaining subscales of MDASI-MM and the EQ-5D summary index scores will also be tabulated.

It is possible that the QoL questionnaires are not completed in line with the visit schedule. An acceptable time delay or “window” during which the questionnaire must be completed is ± 1 week during treatment, at EOT, and the first two visits post treatment, to ensure evaluation of short-term toxicity and response. During follow up for EQ-5D, a wider window (± 3 weeks) would be acceptable after the first two post-treatment visits. A visit window will be assigned to the scheduled visits to ensure that each QoL questionnaire can be assigned to a scheduled visit; for each type of questionnaire the one closest to the schedule visit will be assigned.

For PROs, if a multi item subscale has a missing item, then the average of the remaining items will be used as the Scale score, as long as at least half the items in that Scale are present.

All analyses will be conducted on randomized subjects with baseline and at least one post-baseline assessment.

Descriptive statistics for each instrument will be provided at baseline.

For each instrument, the questionnaire completion rate will be defined as the proportion of questionnaires completed out of the expected number of questionnaires (i.e. the number of subjects randomized for baseline visit and still on treatment for post-baseline visits) at each assessment point (i.e. Screening, Day 1 of each cycle and End of treatment or study withdrawal). The questionnaire completion rate at each assessment point will be presented by treatment group.

By subject listings of the MDASI-MM and the EuroQol Group's EQ-5D data will be provided.

7.11 Healthcare Resource Utilization Data

A separate analysis plan will be developed for economic analyses that will be conducted from this trial. The economic analyses will combine the resource utilization data from the trial with data on unit prices (collected separately) to estimate total costs in preparation for a full-cost analysis.

8 CONVENTIONS

8.1 Baseline Definition

Baseline evaluations will be those performed within 60 days of randomization and prior to first dosing date. When an assessment is repeated multiple times within the screening period, the baseline evaluation will be the one closest to the first dosing date.

Laboratory tests and procedures (ECG, physical measurement and 2D echocardiogram MUGA, skeletal survey and plasmacytoma) done on the first date of dosing will be assumed to have occurred prior to dosing and therefore baseline evaluation for those parameters will be those prior or on the first dosing date.

8.2 Age Definition

Age (years) will be calculated as:

$$\frac{\text{date of informed consent} - \text{date of birth} + 1}{365.25}$$

8.3 Time Since Initial Diagnosis to Randomization Definition

Time from disease diagnosis to randomization (months) will be calculated as:

$$\frac{\text{date of randomization} - \text{date of initial diagnosis} + 1}{30.4375}$$

For the date of cancer diagnosis, the following conventions will be used for imputing partial dates:

- If only the day of the month is missing, the 15th of the month will be used to replace the missing day.
- If the day and month are missing or a date is completely missing, it will be considered as missing.

8.4 Duration and Study Day Definition

In instances in which study period between two dates are to be calculated (for example, duration of response, PFS and OS), the convention to be used is as follows: later date – earlier date + 1 day.

Study day is calculated as assessment date – first dose date + 1 day, if the assessment is taken on or after the first dose day. If the assessment is taken prior to the first dose day, study day will be calculated as assessment date – first dose date. Date of first dose is defined as Study Day 1.

8.5 Day Conversion of Date Imputation

Conversion from days to months or years:

- 1 year = 365.25 days
- 1 month = 30.4375 days

Imputation for partial or missing progression dates:

- If only the day is missing, the 1st of the month will be used to replace the missing day.
- If the day and month are missing or a date is completely missing, the date of progression will be moved back to the last complete tumor assessment date.

In both the cases given above, the imputed date will still be considered an event.

Imputation for partial or missing death dates:

- If only the day is missing, the later of the last known alive date and the 1st of the month will be used to replace the missing day.
- If both the day and the month are missing, the later of the last known alive date and Jan 1st will be used to replace the missing information.

In both the cases given above, the imputed date will still be considered an event.

For partial dates of start of subsequent anti-myeloma therapy, the following conventions will be used:

- When the day is missing, the alternative therapy will be assumed to start on the first day of the given month if this day is later than the last dosing date. Otherwise the alternative therapy will be assumed to start on the day following the last dosing date.
- When the day and the month are missing, the alternative therapy will be assumed to start on the first day of the given year if this day is latter than the last dosing date. Otherwise the alternative therapy will be assumed to start on the day following the last dosing date.

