3.6.1 Withdrawal of Consent

Subjects should be encouraged to continue participation in the trial until the laboratory definition of disease progression is met ([Appendix 6](#)). **Subjects who discontinue study therapy before progression (eg, due to toxicity) should be encouraged to allow the necessary laboratory results (eg, M-protein data, sFLC data, radiologic data, calcium results) to be collected until disease progression criteria are fulfilled, even if the subject is on subsequent therapy (see [Section 8.3.1](#)).** Central laboratory assessments are preferred; however assessments may also be completed locally. Local lab data can be obtained by the subjects' local health care provider or the site staff. Site staff will enter local lab data into the CRF/database. Withdrawal of consent should be minimized because:

1. The subject in this trial who discontinues study therapy before progression will most likely be followed by a healthcare provider locally or at the site via routine standard of care assessments (ie, monthly M-protein data, calcium, etc) and

2. In most cases, this protocol would not require any additional samples beyond those considered standard of care.

If there is uncertainty about the disease progression criteria, investigators are encouraged to contact the BMS Medical Monitor/study director prior to:

1. starting a subject on another myeloma regimen or
2. performing the end of treatment visit for progression

Subjects who request to discontinue study drug will remain in the study and must continue protocol specified follow-up procedures. The only exception to this is when a subject specifically withdraws consent for any further contact with him/her or persons previously authorized by subject to provide this information. Subjects should notify the investigator of the decision to withdraw consent from future follow-up **in writing**, whenever possible. The withdrawal of consent should be explained in detail in the medical records by the investigator as to whether the withdrawal is from further:

1. Study medication but subject is willing to continue to perform visits for PFS follow-up.
2. Study medication and study visits for PFS but agrees to provide the results of future myeloma assessments from another site/local site.
3. Study treatments and results from another site/local sites, but agrees to be contacted for overall survival follow-up.

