4.1.1.3 Primary Definition of Progression-Free Survival (PFS)

PFS will be primarily analyzed applying an intent-to-treat (ITT) definition that utilizes all of the data on each randomly assigned subject at the time of the PFS analysis. PFS will be defined as the time from randomization to the date of the first documented tumor progression or death due to any cause. Clinical deterioration will not be considered progression. A subject who neither progresses nor dies will be censored on the date of their last adequate tumor assessment. A subject who does not have any post-baseline tumor assessments and who has not died will be censored on the date of randomization.

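### The SAP's imputation rules for incomplete progression dates have no lower bound, so a PFS event can be dated before randomization or before an assessment that ruled progression out

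*SAP*

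**What the plan says.** SAP 8.5 has two rules for incomplete progression dates. When the month is known: "If only the day is missing, the 1st of the month will be used to replace the missing day". When day and month, or the whole date, are missing, "the date of progression will be moved back to the last complete tumor assessment date". It then adds: "In both the cases given above, the imputed date will still be considered an event".

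The same section treats two other dates differently. For a death with a missing day, "the later of the last known alive date and the 1st of the month will be used to replace the missing day". For subsequent anti-myeloma therapy, the 1st of the month applies only if it is later than the last dose: "Otherwise the alternative therapy will be assumed to start on the day following the last dosing date". Both rules therefore carry a floor.

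The imputed progression date feeds the primary endpoint. SAP 4.1.1.3 states: "PFS will be defined as the time from randomization to the date of the first documented tumor progression or death due to any cause". SAP 4.1.1.1 describes an adequate assessment as one with enough information to exclude progression. The fallback to the randomization date in SAP 4.1.1.3 and 4.1.1.4 applies to censored subjects only. SAP 8.4 computes durations, PFS included, as the later date minus the earlier date plus one day.

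**The concern.** A progression found at an assessment happened after the previous assessment that excluded it, and after randomization. An imputation rule should respect both limits. The 1st-of-month rule respects neither. The last-assessment rule puts the event on a day when, normally, the subject was shown not to have progressed. If the only complete assessment was at screening, it puts the event before randomization.

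At stake is the internal consistency of the primary endpoint. A record whose event precedes its time origin has no defined handling, so two programmers could produce different PFS times from the same data. The trial is open-label with investigator-assessed PFS, so a correction improvised at analysis would be made with treatment arm and outcome known.

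**Working it through.** **The plan's own figure.** SAP 5.1 asks for at least 71 PFS events for 85% power at HR 0.57, two-sided α = 0.2. With z = 1.2816 + 1.0364 = 2.3180 and 1:1 allocation (assumed, because the design section is redacted):
- Schoenfeld: 4 × 2.3180² / (ln 0.57)² = 68.02, so 69 events.
- Freedman: 2.3180² × (1.57/0.43)² = 71.6, so 72 events.

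The stated 71 lies between them. The imputation rule does not affect this number.

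**Inputs.**
- Assessment interval: 4 weeks (Protocol 3.5 gives it for follow-up after early discontinuation; Protocol 5.4.1 says the same schedule continues after study drug stops).
- Baseline efficacy assessments: up to 28 days before randomization (SAP 6.1).
- Control median PFS: 4.0 months; 114 subjects accrued over about 9 months (SAP 5.1).

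**How often the 1st-of-month rule gives an impossible date.** Let the true progression fall on day D of its month, and let the anchor (the previous progression-free assessment, or randomization) lie g days earlier. The rule moves the date back by D − 1 days, so the imputed date falls strictly before the anchor when D − 1 > g. Counting over the 1,461 days of a four-year cycle:

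| Gap g (days) | Days D affected | Count | Share | Largest overshoot |
|---|---|---|---|---|
| 31 or more | none | 0 | 0% | none |
| 28 | 30–31 | 44 + 28 = 72 | 4.9% | 2 days |
| 25 | 27–31 | 213 | 14.6% | 5 days |
| 21 | 23–31 | 405 | 27.7% | 9 days |

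At 28 days a further 45 dates (3.1%) land exactly on the anchor.

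**Two examples at a 28-day gap.**
- Randomized 3 March, progression 31 March: imputed 1 March, 2 days before randomization.
- Negative assessment 3 July, progression 31 July: imputed 1 July, 2 days before the assessment that excluded progression.

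**What SAP 8.4 does with the March case.** The true PFS is 31 − 3 + 1 = 29 days. Later minus earlier plus one gives 3 − 1 + 1 = 3 days, a plausible-looking value that hides the error. Event minus randomization plus one gives 1 − 3 + 1 = −1 day, for which there is no rule.

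**The last-assessment rule.** The event coincides with the last complete assessment and does not precede it. If that assessment was at screening, the event falls up to 28 days before randomization.

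**Effect on the trial.** A simulation of 2,000 trials assumed 57 subjects per arm, accrual over 274 days, exponential PFS with control median 4.0 months and HR 0.57, visits every 28 days ±3 days, analysis at 71 events and an unstratified log-rank test. All events were treated as progressions, and the share with a missing day was equal in both arms. Only the 1st-of-month rule was simulated.

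| Share with day missing | Imputed events per trial | Before a prior assessment | Before randomization | Power as written | Power with floor |
|---|---|---|---|---|---|
| 0% | 0 | 0 | 0 | 86.0% | 86.0% |
| 5% | 3.50 | 0.20 | 0.02 | 85.9% | 85.9% |
| 10% | 7.05 | 0.41 | 0.04 | 85.7% | 85.7% |
| 20% | 14.15 | 0.80 | 0.08 | 85.7% | 85.8% |

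The missing shares are assumptions; the documents give none.

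**The case against.** The best case against acting is that very little changes. On a strict 28-day schedule few dates are affected, by one or two days, and fewer than one event per simulated trial is dated before a prior assessment. Partial dates may also be rare: the main efficacy tests go to a central laboratory (Protocol 5.4 and 5.9), site staff enter local results in the CRF (Protocol 3.6.1), and SAP 4.1.1.2 says investigators report the earliest measurement date supporting progression. The subject listing in SAP 7.5.1.1 would show odd durations. All of this stands as to size. It does not supply the missing rule, and that listing need not flag imputed dates.

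A reader might infer more than the documents support:

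- **That the average backdating measures the defect.** Setting dates to the 1st moves them 14.73 days earlier on average, but that belongs to the convention. With a floor at a 28-day gap the average is still 14.58 days, so the floor removes 0.15 days. Likewise, a floor moves the last-assessment rule by only one day.
- **That progression could be dated before the response it ends.** Protocol 5.4.2 and 5.4.4 require two consecutive assessments for a response. At 4-week visits, progression then comes about 56 days (2 × 28) after the first documented response, while the 1st-of-month rule moves a date back by at most 30 days.
- **That the error favours one arm.** Protocol 3.6.1 does allow outside data after early discontinuation ("Local lab data can be obtained by the subjects' local health care provider or the site staff"). Nothing shows that partial dates cluster there or differ by arm, and unequal missingness was not simulated.
- **That PFS will come out zero or negative.** Read literally, the SAP 8.4 formula always returns at least one day. The supportable statement is that the handling is undefined.

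**Conclusion.** The gap is real and small. The day-missing rule can date a primary-endpoint event before randomization or before an adequate assessment that excluded progression: 4.9% of calendar dates at a 28-day gap, by at most 2 days, and more at shorter gaps. The rule for a missing day and month puts the event on the last complete assessment, and before randomization only when that assessment was at screening. No visible text supplies a floor for progression or says how to treat an event dated before randomization. The floors for death and subsequent therapy in the same section suggest an oversight.

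The shares assume progression dates spread evenly over the calendar. The finding of negligible effect on power rests on balanced missingness of 5% to 20% and on the simulation settings above. The reason to act is that the primary endpoint should not contain impossible dates, not that the trial loses power.

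**What to change.** Amend SAP 8.5 as follows, before the PFS analysis.

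- **Day missing:** use the later of the 1st of the month and the day after the last adequate progression-free assessment, or the day after randomization if there is no post-baseline assessment.
- **Day and month, or whole date, missing:** use the day after the last adequate progression-free assessment, or the day after randomization if there is none.
- **Both rules:** cap the result at the date of death and the data cut-off. Use the term adequate, as defined in SAP 4.1.1.1, in place of complete.
- **Listing:** show every imputed progression date with the reported partial date and the rule applied.

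No imputed event can then fall on or before randomization or a prior progression-free assessment, so SAP 8.4 can stay as it is. The cost is a few sentences of SAP text, a small programming change and one listing. The 71-event requirement, the sample size and data collection are unaffected.
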